9. DATA COLLECTION & STUDY EVALUATIONS

Medical records will be reviewed prior to “Baseline Study Visit” to confirm study eligibility. After obtaining consent, socio-demographic data will be collected through chart review and interviews. Clinical data that will be collected include but not limited to bladder cancer treatment history, tumor characteristics, stage, laboratory results, medications and co-morbidity.

Study team member or clinic staff will measure height, weight, and vital signs at each specific study time point. Research blood will be drawn at each study time point. Blood and tissue samples may be banked under the optional study (HSC20050234H GU Tissue Bank). For those participants who declined to participate in the optional study, any leftover samples will be permanently de-identified through the GU Tissue Bank (HSC20050234H) honest broker system. At the close of this study, all biological materials collected will be rolled into HSC20050234 GU Tissue Bank.

9.1 Feasibility: We will report recruitment, visit dates, adherence, attrition rates and compliance with randomization for each arm of the study

9.2 Bladder-intact survival: We will report proportion of patients who failed chemoradiation and required salvage cystectomy

9.3 Quality of life: A self-assessment questionnaire using the European Organization for Research and Treatment of Cancer (EORTC) QLQ- C30 and FACT-Bladder will be used for QOL assessment at baseline, 3, 6, 9 and 12 months.⁸

9.4 Progression free survival: This will be measured from the date of finishing chemoradiation or radical cystectomy to the date of first documentation of progression. Progression will be determined using RECIST 1.1 criteria by the treating physician based on radiographic or pathologic evidence of disease progression, or death from disease. Any documented recurrence will be considered progression.⁹ The date of progression will be recorded.

9.5 Candidate gene expression analysis: For the participants who have consented to be part of the optional study (“GU Tissue Bank HSC20050234H), a microarray analysis will be performed on all bladder tumor specimens using Agilent Technologies (Agilent SurePrint G3 Human Gene Expression 8x60K v2) Microarray. Goal is to study the landscape of 50 important candidate genes, which are involved in bladder cancer (for example-BRAF, KRAS, EGFR, FGFR).

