9.6 Activities of Daily Living (ADL) scores: This will be measured at baseline, and during all subsequent follow-up visit (i.e. 3, 6, 9 And 12 months) using Activities of Daily Living QOL Questionnaire using Katz Index of Independence in Activities of Daily Living (ADL).¹⁰

9.7 Retrospective screening & chart review: We will screen and review charts of “potential participant” retrospectively using the latest approved eligibility criteria and study schema to determine:

1. the number of “would-be potential participants”
2. the number of those who were initially deemed eligible and was truly eligible after TURBT
3. the number of those who were initially deemed eligible but was ultimately ineligible after TURBT

4. rationale for ineligibility

The retrospective screen & chart review will start from the date when the study was first approved by the IRB (i.e. April 15, 2016) until present time. Data including but not limited to medical record number, initials of name, gender, race, ethnicity, TURBT result, age at time of treatment, treatment received, date of treatment, eligibility status for the study, and rationale if deemed ineligible, will be captured. We do not intend to contact these patients for study enrollment since they would've received treatments for their diagnosis already. Our intention for this retrospective data collection is that it will provide further insight and information on the potentiality of chemoradiation as treatment modality for patients with specific bladder cancer diagnosis. We need to capture this data in order to represent total population of patients screened, thereby determining the denominator of the study population.

9. 8 Outline of Captured Data

Outcome of Interest	Measure	Method of Assessment
Demographics		Self-report questionnaire
Health History including height, weight, and vital signs		Physical exam, review of EPIC
Study Processes		
recruitment rate adherence attrition feasibility bladder intact survival safety		
Outcomes of interest		
Quality of Life	EORTC	Self-report questionnaire
	FACT-BI	Self-report questionnaire
ADL	Katz ADL	Self-report questionnaire
Progression free survival	RECIST 1.1	Physician assessment
Candidate gene expression	Candidate genes	Laboratory analysis of blood and tissue

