10.4 Assuring Compliance with Protocol and Data Accuracy

As with all studies conducted at CTRC, the PI has ultimate responsibility for ensuring protocol compliance, data accuracy/integrity and responding to recommendations that emanate from monitoring activities. Source verification of data will be performed every twelve week. Protocol compliance, data accuracy and reporting of events is further ensured by an annual audit conducted by the Data Safety Officer, whose audit report is shared with the PI, the research team, and will be reviewed by the CTRC DSMC.

11. STATISTICAL CONSIDERATIONS:

For this pilot non-inferiority study, we aim to randomize **30** evaluable patients (**radical cystectomy: n=15, chemoradiation: n=15**).

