Categorical outcomes will be summarized with frequencies and percentages. Continuously distributed outcomes will be summarized with the sample size, mean, standard deviation, median, minimum and maximum. A consort diagram giving the number patients screened, the number of screen failures, the number randomized, the number lost to follow-up by reason, and the number completing the study by treatment arm will be created. In Aim 1a we will test the hypothesis that chemoradiation therapy is non-inferior to radical cystectomy with regard to change in quality of life at 36 months relative to baseline. In Aim 1b, we will test the hypothesis that chemoradiation is non-inferior to radical cystectomy with regard progression free survival and bladder intact survival. With regard to Aim 1a, assuming the 50% (p_2) of patients randomized to radical cystectomy and 60% (p_1) of patients randomized to chemoradiation will experience improvement in quality of life at 3 years relative to baseline and a 5% margin (Δ) of non-inferiority, this study would require $n=171$ subjects per group to attain 80% power for testing $H_0: p_1 - p_2 \leq \Delta$ versus $H_1: p_1 - p_2 > \Delta$ with $\alpha=5\%$. The non-inferiority of chemoradiation compared with radical cystectomy with regard to changes in quality of life (Aim 1a) will be assessed with Fisher's exact test. Progression free and bladder-intact survival (Aim 1b) will be summarized by treatment arm with Kaplan-Meier curves and supporting tabulations and non-inferiority will be assessed with a logrank test. The significance of treatment arm differences with regard to biomarkers (Aim 2a) will be assessed with t-tests or Wilcoxon tests. Pairwise correlations between biomarkers will be displayed overall and by treatment arm. Logistic regression will be used to find a best linear predictor of treatment arm in terms of multiple biomarkers. Biomarkers may be log transformed prior to analysis. Feasibility (Aim 2b) will be assessed with a new power and sample size calculation. If the logistic regression model fails in Aim 2a, random forests will be attempted. If the logrank test fails in Aim 1b, Fisher's exact test will be used. R (v3+, Vienna, Austria) or SAS (SAS Institute, Cary, North Carolina) software will be used throughout.

REFERENCES

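### Aim 1a non-inferiority is tested with Fisher's exact test, which ignores the 5-point margin; the hypotheses appear to lack a minus sign, and α = 5% has no stated sidedness

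*Combined protocol and SAP*

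**What the plan says.** Section 11 (Statistical Considerations) opens "For this pilot non-inferiority study, we aim to randomize" 30 evaluable patients, 15 per arm. For Aim 1a it assumes that 50% of cystectomy patients (p2) and 60% of chemoradiation patients (p1) "will experience improvement in quality of life at 3 years relative to baseline and a 5% margin", labelled Δ. It gives 171 "subjects per group to attain 80% power for testing" H0: p1 − p2 ≤ Δ against H1: p1 − p2 > Δ. The significance level is written as α = 5%, without saying whether it is one- or two-sided.

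The analysis sentence then states that non-inferiority "with regard to changes in quality of life (Aim 1a) will be assessed with Fisher's exact test". No confidence interval, shifted null or decision rule involving the margin appears in Section 11 or elsewhere.

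Three related statements matter. For Aim 1b, "supporting tabulations and non-inferiority will be assessed with a logrank test", with no margin given. "Feasibility (Aim 2b) will be assessed with a new power and sample size calculation". And the quality-of-life instruments, according to Section 9.3, "will be used for QOL assessment at baseline, 3, 6, 9 and 12 months", although the Aim 1a endpoint is the change at 36 months.

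**The concern.** A non-inferiority claim requires the data to be compared with the margin. The usual Fisher's exact test compares them with zero. A non-significant result does not show that chemoradiation is within 5 points of cystectomy. A significant result in its favour shows superiority to zero, a stricter requirement than the one planned. The plan does not say which outcome would count as non-inferiority.

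This governs the pilot's own prespecified analysis. It also carries forward: the Aim 2b sample size calculation for the larger trial needs a signed margin, a stated α and a test that matches them. Two features of the hypothesis statement could mislead whoever does that calculation: the missing minus before Δ and the missing sidedness.

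**Working it through.** **Inputs (all from Section 11).** p1 = 0.60, p2 = 0.50, margin 5 points, power 80%, α = 5% (sidedness not stated), 171 per group for the planning calculation, 15 per arm in the pilot. The enumerations below use exact binomial probabilities and assume complete data.

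**Step 1: reproduce 171.** With unpooled variance,

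n per group = (z_α + z_0.80)² × [p1(1 − p1) + p2(1 − p2)] / d²

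where d is the distance from the assumed difference (0.10) to the null boundary, and the variance term is 0.24 + 0.25 = 0.49.

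- Boundary −0.05, so d = 0.15, one-sided 2.5%: (1.960 + 0.842)² × 0.49 / 0.0225 = 170.93, rounded up to **171**. The plan's figure is reproduced.
- Boundary −0.05, one-sided 5%: 134.64, rounded up to **135**. Keeping 171 would give 87.6% power.
- Boundary +0.05 as printed, so d = 0.05: 1539 (one-sided 2.5%) or 1212 (one-sided 5%). Under that reading 171 per group has 15% or 24% power.

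The intended calculation is therefore a −0.05 boundary at one-sided 2.5%. The number is right; the hypotheses and the α statement do not say what produced it.

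**Step 2: Fisher's test in the pilot.** 15 per arm, two-sided 5%, cystectomy at 50%:

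| True chemoradiation rate | Fisher significant | Fisher non-significant |
|---|---|---|
| 60% (planned scenario) | 3.3% | 96.7% |
| 45% (exactly at the margin) | 2.0% | 98.0% |
| 35% (15 points worse) | 5.7% | 94.3% |

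Non-significance is almost certain in all three cases, so it does not separate acceptable from unacceptable treatment.

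**Step 3: Fisher's test at the planned size.** At 171 per group with 60% vs 50%, Fisher rejects zero difference with probability 41.5%. The rule that the lower two-sided 95% limit for p1 − p2 must exceed −0.05 succeeds with probability 79.7% (the same for Wald and Newcombe intervals), and with probability 2.5% when the truth is 45% vs 50%.

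An example: 103/171 vs 86/171 is a difference of 17/171 = 9.9 points with a lower 95% limit of −0.5 points. That is non-inferior at a 5-point margin, yet the two-sided Fisher p-value is 0.082.

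**Step 4: the one-sided 5% alternative.** At 135 per group, requiring the lower limit of the 90% Wald interval to exceed −0.05 gives 80.5% power and 5.3% false positives at the margin.

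**Step 5: the margin rule in the pilot.** At 15 per arm the 95% rule has 13.8% power (Wald) or 13.4% (Newcombe). The expected half-width is 1.96 × √(0.49/15) = 0.354, about 35 points. The pilot can estimate the difference but cannot settle it.

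**The case against.** The strongest reply is that the plan never says a non-significant Fisher result means non-inferiority. If significance in favour of chemoradiation is required, the test is conservative: rejecting zero in that direction implies exceeding −0.05. At 15 per arm, one-sided 2.5% Fisher favours chemoradiation with probability only 0.4% at 45% vs 50%. That is correct, and under this reading the fault is lost power, not false success. It does not rescue the plan: power at 171 per group would be about half the stated 80%, the margin would still play no part, and the reader is not told which reading applies.

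It can also be said that the sign is close to typographical. That is largely fair. Δ is called a non-inferiority margin, 171 reproduces only with −0.05, Δ may have been meant as a negative number, and a minus lost when the PDF was read cannot be fully excluded. The +0.05 figures only show what the literal text would imply. The sidedness can likewise be recovered from 171, but only by back-calculation.

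Finally, this is a 30-patient feasibility pilot, and no test would let it decide Aim 1a. That limits the practical effect, but the Fisher sentence is still a prespecified analysis of this study. One further remark stands: Section 9.3 names two instruments, and the plan gives no threshold for improvement, so the proportions need a definition before any interval can be computed.

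**Conclusion.** The point holds and should be fixed. The Aim 1a test does not use the margin, and no decision rule is given. Depending on the reading, the analysis either declares success almost regardless of the truth (94% to 98% in the pilot scenarios examined) or has 41.5% power where 80% was planned. The sample size of 171 is not wrong; it rests on a −0.05 boundary and one-sided 2.5%, neither of which is written down. These figures take the plan's 50% and 60% rates (with 45% and 35% as alternatives for chemoradiation) and complete data.

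The sign and sidedness are lesser wording faults, relevant mainly to the later trial. The Aim 1b logrank sentence, which states no margin, needs the same kind of repair; no figures are offered for it here.

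**What to change.** In Section 11:

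- Replace Fisher's exact test as the Aim 1a criterion with, for example: non-inferiority is concluded if the lower limit of the two-sided 95% confidence interval for p1 − p2 is above −0.05. Name the interval method and define improvement (instrument and threshold).
- Write H0: p1 − p2 ≤ −0.05 versus H1: p1 − p2 > −0.05.
- State one-sided α = 2.5% (two-sided 5%) with 171 per group, which matches the existing figure. If one-sided 5% was intended, state 135 per group and use the two-sided 90% interval.
- Say that this number is a planning figure for the later trial, that the pilot stays at 30, and that its Aim 1a result is reported mainly as an estimate with its interval.
- Give Aim 1b a margin and a matching criterion.

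Separately, reconcile the 12-month schedules in Section 9.3 and Section 9.6 ("during all subsequent follow-up visit (i.e. 3, 6, 9 And 12 months") with Section 7.1, both calendars in Section 8 and the 36-month endpoint.

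The cost is wording, the missing definitions and a standard confidence interval in place of one test. No patients or visits are added: Section 7.1 and both calendars already carry questionnaires to 36 months.

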3.3 Randomization Procedure

A total of 30 patients will be randomized to either chemoradiation group (n=15) or radical cystectomy (with or without neoadjuvant chemotherapy group, n=15). Permuted block randomization process through sequentially numbered, opaque sealed envelopes will be utilized in assigning participants into either radical cystectomy or chemoradiation group. All subjects will be randomized in blocks of size 2. A randomization list containing sequence numbers and treatment assignments will be prepared by the statistician and used as the sole basis for treatment assignments throughout the study.

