8. STUDY CALENDAR

8.1 RADICAL CYSTECTOMY ARM

	Initial visit	Pre-Treatment (tx) TURBT	Baseline	Treatment Period: Radical Cystectomy	Post-tx 3 mon f/u ± 1 mon	Post-tx 6 mon f/u ± 1 mon	Post-tx 9 mon f/u ± 1 mon	Post-tx 12 mon f/u ± 1 mon	Post-tx 18 mon f/u ± 1 mon	Post-tx 24 mon f/u ± 1 mon	Post-tx 30 mon f/u ± 1 mon	Post-tx 36 mon f/u ± 1 mon (end of study visit)		
Study eligibility	X		X											
Informed consent	X													
Assessment of AE						X	X	X	X	X	X	X	X	X
SOC Image studies (X-Ray, CT, and/or MRI)			X			X	X	X	X	X	X	X	X	X
Research blood sample			X			X	X	X	X	X	X	X	X	X
Ht, Wt, and Vitals [#]			X			X	X	X	X	X	X	X	X	X
Research Study Questionnaires			X			X	X	X	X	X*	X*	X*	X*	X*

Note:

SOC = Standard of Care

[#] information may be extracted from EMR

*Research study questionnaire may be emailed or mailed per patient's stated preference

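### Aim 1a compares quality of life only as improved or not improved at month 36 by an unadjusted Fisher's test; a baseline-adjusted score analysis should be added for estimation

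*Combined protocol and SAP*

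**What the plan says.** Section 11 frames Aim 1a as non-inferiority in "change in quality of life at 36 months relative to baseline". The sample size argument turns this into a proportion, "assuming the 50% (p_2) of patients randomized to radical cystectomy and 60% (p_1) of patients randomized to chemoradiation", who "will experience improvement in quality of life at 3 years relative to baseline". It uses "a 5% margin (Δ) of non-inferiority" and concludes that "this study would require $n=171$ subjects per group to attain 80% power". The stated analysis is that "changes in quality of life (Aim 1a) will be assessed with Fisher's exact test". Section 3.3 fixes the actual size: "A total of 30 patients will be randomized to either chemoradiation group (n=15) or radical cystectomy".

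Section 11 names no covariate, no analysis of covariance and no repeated-measures model for quality of life. It does plan descriptive summaries of continuous outcomes, including mean and SD.

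On data collection the document disagrees with itself. Section 9.3 lists EORTC QLQ-C30 and FACT-Bladder at baseline and months 3, 6, 9 and 12, which is five time points. Section 7.1 asks for questionnaires at the post-treatment visits, which run to month 36, and the "Research Study Questionnaires" row in the Section 8 calendars is also marked beyond month 12. Baseline plus eight visits makes nine time points. No section says which of the two instruments is primary or what size of change counts as improvement.

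**The concern.** Both instruments give scores. Fisher's test needs a two-by-two table, so each patient contributes one yes/no at one visit. The size of the change is lost. A patient's starting score serves only to define the change and does not explain variation between patients. The intermediate scores are used in no comparison.

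This matters because the pilot exists to inform a larger trial. Section 11 says that feasibility (Aim 2b) will be judged through a new power and sample size calculation. For quality of life, the planned comparison feeds that calculation with two proportions from 15 patients each. An adjusted score analysis would supply a more precise arm contrast, the residual SD and the baseline-to-follow-up correlation, all from questionnaires that the calendars already schedule.

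**Working it through.** **Inputs from the documents.** Improvement rates 0.50 (cystectomy) and 0.60 (chemoradiation), margin 0.05, 80% power, alpha 5% with sidedness unstated, 171 per group (all Section 11); 15 per arm (Section 3.3). **Assumptions, not in the documents.** A normal change score, and a baseline-to-month-36 correlation r of 0.3 to 0.7 with equal variances at the two times.

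**1. The plan's own figure.** With unpooled variance and a one-sided 2.5% level:

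n = (1.960 + 0.842)² × (0.6×0.4 + 0.5×0.5) / (0.10 + 0.05)² = 7.849 × 0.49 / 0.0225 = 170.9, so 171.

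This reproduces. (One-sided 5% gives 135.) The stated size is therefore a two-proportion calculation, which confirms that the endpoint is binary.

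**2. Information kept by the binary cut.** For a normal score cut so that a proportion p improves, relative efficiency is φ(z_p)² / [p(1−p)].

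| p | kept | lost |
|---|---|---|
| 0.50 | 0.637 | 36.3% |
| 0.55 | 0.633 | 36.7% |
| 0.60 | 0.622 | 37.8% |

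At p = 0.55, 15 patients behave like 0.633 × 15 = 9.5.

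**3. Sensitivity to normality.** For a median split, efficiency against the mean is 4f(0)²σ². It is 0.82 for a logistic score (18% lost), 0.96 for t with 5 df (4% lost), and 2.0 for a Laplace score (nothing lost).

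**4. Baseline as covariate.** Variance of the adjusted estimate relative to the raw change score is (1−r²) / [2(1−r)] = (1+r)/2. This is 0.65, 0.75 and 0.85 for r = 0.3, 0.5 and 0.7, a reduction of 35%, 25% and 15%.

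**5. Precision of the planned contrast.** Half-width = 1.96 × √(0.49/15) = 0.354, or about 35 points. That is seven times the 5-point margin.

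**6. What it could mean for a larger trial.** On the latent normal scale, the effect is z(0.60) − z(0.50) = 0.253 SD and the margin is z(0.50) − z(0.45) = 0.126 SD, 0.379 SD in total.

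n = 2 × 7.849 / 0.379² = 109.3, so 110 per group in place of 171 (36% fewer).

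Multiplying by (1+r)/2 gives 72, 82 and 93 per group for r = 0.3, 0.5 and 0.7 (58%, 52% and 46% fewer than 171). The score-scale margin here is a translation for illustration; the plan sets none.

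**7. Non-inferiority power at 15 per arm.** Normal approximation, one-sided 2.5%:

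- Binary: Φ(0.15/0.181 − 1.96) = 13%.
- Change score: Φ(0.379/0.365 − 1.96) = 18%.
- Baseline-adjusted: 20% (r = 0.7) to 25% (r = 0.3).

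**The case against.** The strongest reply is that nothing in this pilot turns on the choice. Power for the quality-of-life hypothesis is about 13% as planned and 18-25% with the alternatives. The plan itself says that 171 per group are needed. A score-scale result also has no pre-set margin, so it cannot answer the non-inferiority question. All of this stands. The case for the change is estimation and planning.

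A reader might also infer more than the documents support:

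- *That baseline is ignored.* The outcome is already a change from baseline. What is missing is baseline as a covariate.
- *That the pilot will yield no SD.* Section 11 plans descriptive SDs for continuous outcomes. The unplanned items are the adjusted difference with its interval, the residual SD and the correlation.
- *That patients without a month-36 form will be dropped.* Section 11 gives no rule for missing quality-of-life data. The gap is silence.
- *That over a third of the information is lost outright.* This depends on normality, and the documents give no score distribution.
- *That nine sets of scores are certain to exist.* Section 9.3 stops at month 12. If it governs, neither the planned test nor a month-36 score analysis has data.

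A repeated-measures model is not free either. An unstructured covariance over eight visits has 8×9/2 = 36 parameters for at most 30 patients. Deaths before month 36 will matter: Section 1.1.1 cites three-year disease-specific survival of 74% and 50% in complete and incomplete responders with T2 disease. A likelihood model would implicitly carry scores past death. These objections shape the remedy but do not remove the point.

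**Conclusion.** The point holds in a limited form. As written, the arms are compared on quality of life only through an unadjusted two-by-two test at month 36. The cost is about 36-38% of the information if the change score is near normal, and less if its tails are heavier. Covariate adjustment would remove a further 15-35% of the change-score variance, for assumed correlations of 0.7 down to 0.3. On the same assumptions, the choice could move a future trial from 171 per group to 110, or to 72-93 with baseline adjustment.

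The figures do not show that the pilot becomes adequately powered or that its conclusions would change. The addition is worth making because it is cheap and serves Aim 2b directly.

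**What to change.** 1. Reconcile Section 9.3 with Section 7.1 and the Section 8 calendars on how long quality of life is collected, and name one primary scale.
2. Add to Section 11, labelled as estimation, an analysis of covariance of the month-36 score on arm and baseline score. The alternative is a repeated-measures model over the scheduled visits with a parsimonious covariance structure, its missing-at-random assumption stated.
3. Under either method, report deaths before month 36 by arm and handle them separately from missing forms.
4. Report the adjusted arm difference with 95% CI, the residual SD and the baseline-to-follow-up correlation, and carry them into the Aim 2b calculation. With 30 patients at most, the SD and correlation will be imprecise, so that calculation should use a range.
5. Keep the responder proportion with its 5-point margin. How that margin should be tested is a separate matter.

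The cost is about one paragraph in Section 11, a correction to the collection schedule and a little more analysis. If the calendars are confirmed, no extra data are needed. The downside is that the score-scale result has no pre-set margin and is an estimate only.

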1. BACKGROUND AND SIGNIFICANCE

Radical cystectomy is the gold standard treatment for muscle-invasive bladder cancer. It involves removal of the bladder and prostate for men and anterior exenteration (including the bladder, uterus, ovaries, and part of the vagina) for women. Patients who were treated with the surgical approach report poor overall satisfaction, sexual function, urinary and bowel function, and health-related quality of life. The current NCCN (National Comprehensive Cancer Network) Clinical Practice Guidelines (version 2.2015) indicates bladder-preserving therapy with cystectomy reserved for tumor recurrence represents a safe and effective alternative to immediate radical cystectomy for muscle invasive bladder cancer.

According to the current NCCN guidelines, patients who are not surgical candidates (i.e. those with extensive comorbidities and/or poor performance status), chemoradiation can be used as a curative treatment regimen. This bladder-sparing therapy consist of (1) maximal transurethral resection of bladder tumor (TURBT), (2) induction external-beam radiation therapy with concurrent chemotherapy, (3) cystoscopic assessment of treatment response with prompt cystectomy for non-responders, and (4) active cystoscopic surveillance with salvage cystectomy at the first sign of invasive recurrence.

Retrospective studies have shown that the majority of chemoradiation patients achieves a clinical response and preserves the native bladder in >70% of patients while offering long-term survival rates comparable to contemporary cystectomy series.^{1,2}

We hypothesize that chemoradiation is non-inferior to radical cystectomy with regard to quality of life and progression free and bladder intact survival. Short of a randomized trial, any direct comparison of chemoradiation to radical cystectomy to address our hypothesis is difficult and must account for selection bias and confounding variables resulting from discordance between clinical, pathologic staging, functional status and comorbidities. Our proposed randomized pilot non-inferiority study aims to provide feasibility data for a larger randomized clinical non-inferiority trial comparing the efficacy and safety of chemoradiation and radical cystectomy.

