4.3. Required Evaluations/Management (baseline prior to initiation of any protocol treatment)

- a) Cystoscopic evaluation by the participating urologic surgeon no more than 6 weeks prior to registration will include bimanual examination under anesthesia, as thorough as possible, a transurethral resection of the bladder tumor. Patients referred from an outside hospital with a muscularis propria-invading bladder tumor will be re-resected by the participating urologist.
- b) Radiologic evaluation including chest CT, abdominal and pelvic CT and bone scan no more than 6 weeks prior to start of treatment.
- c) Comprehensive metabolic panel (CMP) obtained no more than 4-6 weeks prior to registration

5. Randomization

5.1 Radical Cystectomy Arm- Those randomized to “Radical Cystectomy” will be scheduled for surgery. In brief, radical cystectomy is the removal of the entire bladder, nearby lymph nodes (lymphadenectomy), part of the urethra, and nearby organs that may contain cancer cells. In men the prostate, the seminal vesicles, and part of the vas deferens are also removed. In women the cervix, the uterus, the ovaries, the fallopian tubes, and part of the vagina are also removed. Participants in this group may also undergo neoadjuvant chemotherapy prior to the surgery as is the current standard of care. The decision for specific chemotherapy regimen is based on medical oncologist’s evaluation. All AE occurring during the study period will be assessed and attribution assigned.

The surgical approach, robotic versus open, is determined by patient and surgeon mutual preference. All urinary diversions will be done via an open incision and the mode of diversion, whether intracorporeal or extracorporeal (orthotopic neobladder, continent cutaneous diversion or ileal conduit) will be selected by mutual agreement of the surgeon and patient, as is customarily done. The extent of the lymph node dissection will be determined by the surgeon but at minimum will include the external iliac, obturator, and hypogastric regions.

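### The planned between-arm non-inferiority test on bladder-intact survival is decided by how the event is defined, because bladder removal is the assigned treatment in one arm

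*Combined protocol and SAP*

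**What the plan says.** Section 11 sets out a formal hypothesis for Aim 1b: "we will test the hypothesis that chemoradiation is non-inferior to radical cystectomy with regard progression free survival and bladder intact survival". On the analysis it says "Progression free and bladder-intact survival (Aim 1b) will be summarized by treatment arm", using Kaplan-Meier curves and tabulations, and that "non-inferiority will be assessed with a logrank test". It adds a fallback: "If the logrank test fails in Aim 1b, Fisher's exact test will be used". The planned size is "radical cystectomy: n=15, chemoradiation: n=15".

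Section 5.1 describes the comparator: "radical cystectomy is the removal of the entire bladder", together with nearby nodes and organs.

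The only description of the endpoint is in Section 9.2: "We will report proportion of patients who failed chemoradiation and required salvage cystectomy". It covers one arm and gives a proportion. It has no time origin, no rule for deaths and no rule for the cystectomy arm. Section 9.4 gives an origin for progression free survival (completion of chemoradiation or of cystectomy). Bladder-intact survival has none.

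**The concern.** A between-arm time-to-event test is informative only if the event can occur in both arms as an outcome. Here, bladder loss in the cystectomy arm is the treatment itself. Either every operated patient counts as an event, or planned cystectomy is excluded and that arm can have no bladder-loss event. The plan does not say which. Section 11 implies a comparison across arms, while Section 9.2 describes a measure that exists in one arm.

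At stake is a small p-value on a stated efficacy hypothesis, in a 30-patient pilot, that would say nothing about which treatment is better. The quantity of real interest is how often, and when, chemoradiation patients keep the bladder while alive. It would rest on an undefined event. Section 1 separates prompt cystectomy for non-responders from salvage cystectomy at invasive recurrence, and Section 6 sends induction non-responders to cystectomy. Whether those early operations count under Section 9.2 is unstated, and it changes the reported rate directly.

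**Working it through.** **The plan's own figure.** None is given for this endpoint. The only sample-size figure, 171 per group, is for quality of life. It reproduces with 5% read as two-sided: (1.960 + 0.842)² × (0.60×0.40 + 0.50×0.50) / (0.10 + 0.05)² = 7.849 × 0.49 / 0.0225 = 170.9. It does not bear on this point.

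**Inputs from the documents.** 15 per arm, logrank with Fisher fallback (Section 11); bladder removed in the cystectomy arm (Section 5.1); chemoradiation "preserves the native bladder in >70% of patients" (Section 1).

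**Assumptions not in the documents.** Surgery at 0.5–2 months, or at 3–6 months to represent neoadjuvant chemotherapy; 60% of chemoradiation losses at 2–4.5 months; no deaths or censoring before month 36.

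**Reading A: planned cystectomy is an event.**

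*Logrank, all 15 operations at the origin, before any chemoradiation loss.* In the chemoradiation arm:
- Observed = 0; expected = 15 × 15/30 = 7.5.
- Variance = 15 × ½ × ½ × (30 − 15)/(30 − 1) = 1.940.
- Z = −7.5/√1.940 = −5.39, two-sided p = 7.2e-8, in favour of chemoradiation.

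Afterwards only chemoradiation patients are at risk, so each later loss has observed equal to expected and adds no variance. Z is the same whether 0, 3, 5, 8, 10 or 12 of 15 chemoradiation patients lose the bladder. If the origin in Section 9.4 were borrowed, every operated cystectomy patient would have the event at time zero.

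*Logrank by simulation (2,000 trials per cell, all cystectomy patients operated).* Share of trials with Z beyond 1.96 in favour of chemoradiation:

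| Surgery at | 70% preserved | 50% preserved | 30% preserved |
|---|---|---|---|
| 0.5–2 months | 100% | 100% | 100% |
| 3–6 months | 99.8% | 94% | 72% |

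If surgery is at 3–6 months and 20% of the cystectomy arm is not operated on (taken to stay bladder-intact to month 36), the share at 70% preservation is about 81%. At 20% preservation with surgery at 3–6 months it is about 52% if all are operated on, and about 7% if 20% are not.

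*Fisher fallback.* With 15/15 losses against 15 − m losses, so that m chemoradiation patients keep the bladder, two-sided p = 2 × C(15, m)/C(30, m):
- 5/15 lost: 2 × 3,003/30,045,015 = 0.0002.
- 10/15 lost: 2 × 3,003/142,506 = 0.042.
- 11/15 lost: 2 × 1,365/27,405 = 0.0996.
- 12/15 lost: 2 × 455/4,060 = 0.22.

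**Reading B: only salvage cystectomy after failed chemoradiation is an event (Section 9.2).** The cystectomy arm has 0/15 by definition. A 30% loss among 15 is 4.5 patients, so 4 or 5 losses match the cited preservation.
- 0/15 v 5/15: Fisher p = 2 × C(15, 5)/C(30, 5) = 2 × 3,003/142,506 = 0.042, against chemoradiation.
- Logrank with losses spread evenly over months 2–12: Z = 2.11 with 4 losses and 2.41 with 5, against chemoradiation.

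**Side by side.** The same chemoradiation result, 5 of 15 bladders lost, gives Fisher p = 0.0002 in favour of chemoradiation under A and p = 0.042 against it under B.

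**The case against.** A reader might infer that the test always favours chemoradiation, so that its result is fixed in advance. The documents do not support that. Nowhere do they say that planned cystectomy is an event, and the one description they give, in Section 9.2, points the other way. Even under Reading A, the result is exact only when operations precede the chemoradiation losses. Neoadjuvant chemotherapy may delay surgery (Sections 2.3 and 5.1). Induction non-responders go to cystectomy after an evaluation 3–4 weeks after induction (Sections 6 and 8.2), so early losses may cluster. Withdrawal is provided for (Section 3.4). With these features and low preservation, the certainty falls well short of 100%, and the Fisher fallback is not significant from 11/15 losses upward. This part of the objection stands.

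A reader might also infer that bladder preservation after chemoradiation is not estimated at all. That is too strong: Section 11 plans Kaplan-Meier curves by arm, which include chemoradiation, and Section 9.2 adds a proportion. What is missing is a usable event and time origin.

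Finally, this is a feasibility pilot, Section 2.2 words Aim 1b as determining and quantifying, and no margin is given for Aim 1b. A plain logrank test could therefore not properly establish non-inferiority for either Aim 1b endpoint. That is true but separate. Section 11 still states a formal hypothesis on this endpoint, and none of these arguments makes the comparison informative.

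**Conclusion.** The point holds in this form: the between-arm test on bladder-intact survival reflects the event definition and not the relative merit of the treatments, and the plan leaves that definition open. If planned cystectomy counts, the test favours chemoradiation almost regardless of its effectiveness. Z is 5.39 when all operations come first. At 70% preservation with everyone operated on, 99.8–100% of simulated trials are significant. If only salvage cystectomy counts, bladder loss can occur only in the chemoradiation arm and can only count against it.

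The logrank at the origin and the Fisher values are exact. The simulated shares rest on assumed surgery times, assumed timing of chemoradiation losses, and no deaths or censoring. Counting deaths would add events to both arms under Reading B but would leave the bladder-loss component one-sided.

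**What to change.** In Section 11, delete the between-arm hypothesis and test for bladder-intact survival, including the Fisher fallback for it. Keep the Aim 1b between-arm comparison for progression free survival.

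Report bladder-intact survival descriptively in the chemoradiation arm only, by Kaplan-Meier, with 95% confidence intervals at 12 and 36 months. Count cystectomy for any reason (including after induction non-response) or death as the event, from one stated origin. Randomisation is a natural choice; if it is used, note that progression free survival in Section 9.4 starts elsewhere. The origin and the two time points are reasonable choices that the documents do not dictate. What matters is that they are fixed before analysis.

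Rewrite Section 9.2 to the same definition, and adjust the hypothesis in Section 1 so that it no longer claims non-inferiority on this endpoint.

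The cost is wording only. Section 6 already records the start date of second-phase treatment and Section 7.1 runs visits to month 36, so no new data are needed. The only loss is a between-arm p-value that carries no information.
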